**RTOG Headquarters\***  
**[name]**  
**Philadelphia, PA 19103**

**\*If a data form is available for web entry, it must be submitted electronically.**

Patients will be identified by initials only (first middle last); if there is no middle initial, a hyphen will be used (first-last). Last names with apostrophes will be identified by the first letter of the last name.

**12.1** Summary of Data Submission (2/16/10)

Item	Due
Demographic Form (A5)	Within 2 weeks of study entry
Initial Evaluation Form (I1)	
Pathology Report (P1)	
Slides/Blocks (P2)	
Charlson Comorbidity Index (CN) and Comorbidity Recording Sheet	

Lung Adverse Event Form (AE)	Within 24 hours of identification of an adverse event, fax to [contact] ; also at 12 months after start of SBRT.
Radiotherapy Form (T1) Copy to HQ and ITC	Within 1 week of RT end
Daily Treatment Record (T5)	Fax to RTOG HQ: [contact], Attn: RT QA on the last day of the patient's treatment or by the end of the next business day, with a copy to ITC  NOTE: If for any reason the assigned course of treatment cannot be completed, RTOG RTQA must be notified at [contact] on the day the patient stops radiation.
Follow-up Form (F1)	Every 3 months in years 1-2; every 6 months in years 3-4, then annually

## **12.2 Summary of Dosimetry Digital Data Submission (Submit to ITC; see Section 12.2.1) [2/16/10]**

Item	Due
Preliminary Dosimetry Information (DD) †Digital Data Submission – Treatment Plan submitted to ITC via SFTP account exported from treatment planning machine by Physicist. Digital data submission includes the following: 
 
• CT data, critical normal structures, all GTV, CTV, and PTV contours
 
• Digital beam geometry for initial and boost beam sets
 
• Doses for initial and boost sets of concurrent treated beams
 
• Digital DVH data for all required critical normal structures, GTV, CTV, and PTVs for total dose plan (DV)
 
	Within 1 week of start of RT
Digital Data Submission Information Form(DDSI) – Submitted online (Form located on ATC web site, http://atc.wustl.edu/forms/DDSI/ddsi.html )  Hard copy isodose distributions for total dose plan as described in QA guidelines† (T6)	
NOTE: Sites must notify ITC via e-mail ( [contact]) after digital data is submitted. The e-mail must include study and case numbers or, if the data is phantom, “dry run” or “benchmark”.	
Final Dosimetry Information	Within 1 week of RT end
Radiotherapy Form (T1) [copy to HQ and ITC] Daily Treatment Record (T5) [copy to HQ and ITC] Modified digital patient data as required through consultation with Image Guided Therapy QA Center	

†Available on the ATC web site, <http://atc.wustl.edu/>

**12.2.1** Digital Data Submission to ITC (2/16/10)

Digital data submission may be accomplished using media or the Internet.

For network submission: The FTP account assigned to the submitting institution by the ITC shall be used, and e-mail identifying the data set(s) being submitted shall be sent to:

[[contact]](mailto:[contact])

For media submission: Please contact the ITC about acceptable media types and formats.

Hardcopies accompanying digital data should be sent by mail or Federal Express and should be addressed to:

**Image-Guided Therapy Center (ITC)**

**ATTN: [name]**

**[name]**

**St. Louis, MO 63108**

**[contact]**

**[contact]**

**13.0 STATISTICAL CONSIDERATIONS**

**13.1 Study Endpoints**

**13.1.1** Primary Endpoint of Phase I Portion (7/27/10)

The maximal tolerated dose (MDT) of SBRT radiation dose associated with a 0.20 probability of dose-limiting toxicity (DLT); DLT is defined as any grade 3 or worse toxicity (per CTCAE, v.4, MedDRA, v. 12.0), that occurs within 1 year from the start of SBRT, is possibly, probably, or definitely related to treatment, and is related to the following specific symptoms:

- Grade 3-5 Cardiac Disorders
  - Pericardial effusion
  - Pericarditis
  - Restrictive cardiomyopathy
- Grade 4-5 Gastrointestinal Disorders
  - Dysphagia
  - Esophagitis
  - Esophageal fistula
  - Esophageal obstruction
  - Esophageal perforation
  - Esophageal stenosis
  - Esophageal ulcer
  - Esophageal hemorrhage
- Grade 3-5 Nervous System Disorders
  - Brachial plexopathy
  - Recurrent laryngeal nerve palsy
  - Myelitis
- Respiratory, Thoracic, and Mediastinal Disorders, Grade 3-5, except as noted below
  - Atelectasis (grade 4-5 only)
  - Bronchopulmonary hemorrhage
  - Mediastinal hemorrhage
  - Pleural hemorrhage
  - Tracheal hemorrhage
  - Bronchial fistula
  - Pulmonary fistula
  - Bronchopleural fistula
  - Tracheal fistula
  - Hypoxia (provided grade 3 is worse than baseline)
  - Bronchial obstruction
  - Tracheal obstruction
  - Pleural effusion
  - Pneumonitis
  - Pulmonary fibrosis

- Changes in Pulmonary Function Tests per the SBRT Pulmonary Toxicity Scale (see Section 6.9.5), Grade 3-5
  - FEV1 decline
  - Forced Vital Capacity decline
- Any Grade 5 adverse event attributed to treatment

All reported serious adverse events (SAEs) listed above will be reviewed by 1 of 3 designated senior radiation/medical oncologists who have expertise in the treatment of lung cancer and who are not associated with this study within 2 business days of receipt of all supporting documentation. The determination of those SAEs as a study DLT will be made by the designated independent reviewer. All reported SAEs listed above will be considered DLTs until reviewed by the designated independent reviewer.

**13.1.2** Primary Endpoint of Phase II Portion (8/20/10)

Two-year primary tumor control rate at the MTD of SBRT (See Section 11.3.3)

**13.1.3** Secondary Endpoints

**13.1.3.1** Progression-Free Survival (see Section 11.3.3);

**13.1.3.2** Overall Survival (see Section 11.3.3);

**13.1.3.3** Local Progression (see Section 11.3.3);

**13.1.3.4** Regional nodal progression (see Section 11.3.3);

**13.1.3.5** Distant metastases (see Section 11.3.3);

**13.1.3.6** Any grade 3 toxicity other than a DLT occurring within the first year;

**13.1.3.7** Late grade 3 toxicity.

**13.1.4** Tertiary Endpoints (Exploratory) [8/20/10]

**13.1.4.1** To study if molecular markers (proteomic or genomic) in the blood circulation will predict 2-year primary tumor control rate, or the occurrence of grade  $\geq 2$  pulmonary adverse events, or the occurrence of grade  $\geq 2$  non-pulmonary adverse events;

**13.1.4.2** To study the prognostic significance of comorbidity status;

**13.1.4.3** To describe the medical physics endpoints of tumor motion and inter-fraction (setup) errors.

**13.2** Justification of Design (7/27/10)

Since this trial will provide an estimate of efficacy for the MTD dose, it can be thought of as a seamless phase I/II trial. Monte Carlo simulation is used to assess the operating characteristics of this trial with respect to each of these metrics in turn. Three simulations were performed for the true dose-conditional probability of toxicity, which are described in Table 13.1. Scenario 1 (DLT-td) is the initial trial design for true dose-conditional probability of toxicity. Scenario 2 (DLT+) is approximately twice as toxic as assumed by the trial design. Scenario 3 is more than twice as toxic as the trial design, with rapidly increasing toxicity at dose Levels 7 and higher (DLT++).

These scenarios are used to assess the robustness of the design to mis-specification of the probabilities of toxicity. The trial assumes that a patient has the same risk of developing a DLT at any point during the 1-year observation period (flat hazard rate). Because of this, the cumulative observation time across patients is acceptable. Within each scenario, this assumption is tested by assessing the operating characteristics of trials where: DLT is equally likely across 1 year (trial assumption); DLT is substantially more likely early in the trial; DLT is substantially more likely late in the trial (see insets, Figure 13.1 below). In 2 completed RTOG trials, 0236 and 0324, which used CTCAE, v. 3.0, the timing of the DLTs as defined in this study was examined during the first year. In both trials, there was no suggestion that the DLTs were more likely to occur later in the risk period. (see Appendix VII for further details). Two hundred and fifty trials were simulated for each of the nine sets of experimental conditions derived from the 3 scenarios and the 3 different hazard rates. The numbers of DLTs, estimated target doses, distribution of doses, and statistical power to identify at least 1 dose as possibly being superior to standard therapy are graphed in Figures 13.1 and 13.2 (below).

**13.2.1** Expected Number of Observed DLTs

The distributions of the number of DLTs observed (out of 75 treated and evaluable patients) for the simulated trials are described in the box plots in Figure 13.1. The boxes indicate the 75th, 50th, and 25th percentiles (from top to bottom), and the stems extend to the 95th and 5th percentiles. The plus indicates the mean. The median number of DLTs ranges from 11 (14.7%) to 18 (24%). If the design assumptions about P(DLT) are correct (DLT-td), over 85% of the simulated trials have less than 15 DLTs (20%), and at least 99% have less than 18, irrespective of the hazard rate. If P(DLT) is under-estimated as in scenarios DLT+ and DLT++, the median number of toxicities for simulated trials in either scenario does not exceed 18, and

the third quartile does not exceed 20 (26.7%). The number of toxicities observed is relatively insensitive to the mis-specification of the hazard rate.

[figure not shown]
**13.2.2** Accuracy of Selection of Target Dose

The distributions of target doses that the trial selects are presented in the right column of Figure 13.1. If the design assumptions about P(DLT) are correct (DLT-td), the trials overwhelmingly pick the correct target dose, indicated by the asterisk (Level 9). If P(DLT) is underestimated as in scenario DLT+ , the target dose is picked within one level of the true target dose (i.e., with  $0.15 \leq P(\text{DLT}) \leq 0.30$ ) in over 90% of the simulated trials. If the P(DLT) is more severely underestimated as in scenario DLT++ , that proportion is higher.

[figure not shown]
**13.2.3** Estimation of Primary Tumor Control (8/20/10)

The average number of patients treated at each dose is displayed in the left column of Figure 13.2. Again, the target dose is denoted by an asterisk. In the DLT-td cases, 7-14 patients are treated at Levels 5-8 due to the starting dose (level 5, 10 Gy) and escalation restrictions. In the DLT+ simulations, 8-14 patients on average are treated on either of the 2 dose levels (8 and 9) with  $P(\text{DLT}) > 0.3$ , which result, on average in 3-5 DLTs. In the DLT++ simulations, 8-15 patients on average are treated on 1 of 3 dose levels (7, 8, and 9) with  $P(\text{DLT}) > 0.3$  which result on average in 4-8 DLTs.

Primary tumor control was modeled as a function of dose by logistic regression model. A one-sided test with a significance level of 0.05 was employed, which is appropriate for a Phase II proof-of-concept trial. The right column of Figure 13.2 (below) assesses the power of the test of the null hypothesis that  $P(\text{primary tumor control}) < 0.7$  at the chosen target dose. For all the simulations, it was assumed that  $p_l = P(\text{primary tumor control} | \text{dose level})$  increased linearly in the regression model between 60% of  $p_9$  at the lowest level, and  $p_9$ , where  $p_9$  is graphed on the lower axis (for instance, trials labeled 0.9 indicated  $P(\text{primary tumor control})$  increased linearly from 0.54 at Level 1 to 0.9 at Level 9, and equaled  $p_6 = 0.83$  at the true target dose). It is seen that, for the (DLT-td) trials, where the most efficacious dose has acceptable toxicity, the power exceeds 80% when  $p_9$  is 0.89 or greater, but that estimated power is more modest for the DLT+ or DLT++ simulations, where the selected target dose, and hence the efficacy at that dose, is lower. For example, with the DLT+ simulations, level 6 was the most frequently selected target dose (~ 40%), while dose levels 8 and 9 were uncommon (~4.5% and ~1.0%) This is an appropriate outcome, because these would be trials where adequate efficacy can only be achieved at unacceptably toxic doses.

**Figure 13.1:** Operating characteristics for observed toxicity and selection of target dose from simulated trials. Inset describes hazard function. DLT-td, DLT+, and DLT++ are specified in Table 13.1. Asterisks indicate true target dose.

**(4/12/12) Figure 13.2:** Distribution of doses and power functions for simulated trials  
 Hazard function changes from top to bottom as in Figure 13.1. DLT-td, DLT+, and DLT++ are specified in Table 13.1 Left column indicates the expected number of patients treated at each dose, while the right-hand column indicates the power to test the null hypothesis that  $P(\text{primary tumor control}) < 0.7$  at the target dose, as the  $P(\text{primary tumor control})$  at Level 9 increases from 0.7 to 0.99 (see Section 13.2.3 for a more detailed description).

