### 1.3.1 Critical Organ Dose-Volume Limits

The aim of this study is to determine the toxicity (i.e., the MTD) of SBRT for centrally located lung tumors. The thoracic organs that are at risk for RT injury (i.e., organs at risk [OARs]) from high SBRT doses and are expected to be determinants of dose-limiting toxicity are lung, central airway/bronchi, esophagus, heart, great vessels, spinal cord, and nerves (as detailed in Section 6.5). If the RT dose-volume limits of these critical organs exposed to high dose per fraction RT were known, there would be no need to perform this dose-seeking study. There is a large body of knowledge on the RT tolerance of those organs to conventionally fractionated RT (1.8-2 Gy per fraction), describing the RT tolerance in terms of volume of the organ irradiated to a certain dose (e.g., V20, volume irradiated to 20 Gy or more) or as mean RT dose to the entire organ. There are clinical studies reporting experience with somewhat hypofractionated RT (e.g., 2.5-3 Gy per fraction), but it is not clear how those dose-volume limits can be converted into limits suitable for this study in which much smaller volumes are irradiated to much higher doses per fraction. Although BED formulas are used to compare different RT dose-fractionation schedules, these formulas may not be appropriate for the extreme hypofractionation (in conjunction with very small volumes irradiated). Of more relevance, particularly in terms of airway tolerance, is the longstanding experience with endobronchial brachytherapy, which demonstrated the safety of large doses per fraction (in the range of 10-15 Gy) to the airway and surrounding structures, with low incidence of radiation bronchitis and/or bronchial stenosis (6% -12%) and isolated cases of fatal hemoptysis in patients with associated progression of their cancer in the airway.

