**Table 3**

Serial Tissue*	Volume	Volume Max (Gy)	Max Point Dose (Gy)	Avoidance Endpoint
Esophagus, non-adjacent wall	<5 cc	27.5 Gy (5.5 Gy/fx)	105% of PTV prescription	stenosis/fistula
Heart/Pericardium	<15 cc	32 Gy (6.4 Gy/fx)	105% of PTV prescription	pericarditis
Great vessels, non-adjacent wall	<10 cc	47 Gy (9.4 Gy/fx)	105% of PTV prescription	aneurysm
Trachea and ipsilateral bronchus, non-adjacent wall	<4 cc	18 Gy (3.6 Gy/fx)	105% of PTV prescription	stenosis/fistula

\*The volume maximum column shows suggested limits for these structures for planning purposes. Exceeded these limits is not a protocol violation. However, exceeding the Maximum Point Dose column is a violation per Section 6.7.2.

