The skin will be defined as the outer 0.5 cm of the body surface. As such it is a rind of uniform thickness (0.5 cm) which envelopes the entire body in the axial planes. The cranial and caudal surface of the superior and inferior limits of the planning CT should not be contoured as skin unless skin is actually present in these locations (e.g., the scalp on the top of the head).
- 6.5.2.10** Great Vessels  
The great vessels (aorta and vena cava, not the pulmonary artery or vein) will be contoured using mediastinal windowing on CT to correspond to the vascular wall and all muscular layers out to the fatty adventitia. The great vessel should be contoured starting at least 10 cm above the superior extent of the PTV and continuing on every CT slice to at least 10 cm below the inferior extent of the PTV. For right sided tumors, the vena cava will be contoured, and for left sided tumors, the aorta will be contoured.

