### **6.9** (2/16/10) Radiation Therapy Adverse Events

The rationale for this phase I/II study is to determine the safe SBRT dose schedule for centrally-located NSCLC, i.e., within the proximal bronchial tree. There is concern about RT effects on organs at risk, most notably central airway, esophagus and heart/pericardium, as these organs

will be in immediate proximity to the centrally-located tumors. **See Section 13.1.1 for definitions of dose-limiting toxicities for this study.**

**6.9.1** Cardiac and Pericardial Injury

Although cardiac and pericardial injury is uncommon in the conventionally fractionated course of RT, with large doses per fraction of SBRT a number of possible side-effects can be seen.

**6.9.2** Gastrointestinal/Esophageal Injury

The radiation effects on the esophagus can be acute: esophagitis (i.e., dysphagia, causing pain on swallowing, typically relatively soon after RT course is completed, and typically resolves on its own within days to a week or longer), or chronic, typically manifesting with dysphagia due to stenosis, or esophageal ulceration, with perforation in the extreme cases.

**6.9.3** Central Airway/Bronchial Injury

This bronchial injury with subsequent focal collapse of lung may impair overall pulmonary status. It also makes further assessment of tumor response more difficult as the collapsed lung approximates the treated tumor. Because atelectatic lung and tumor have similar imaging characteristics, radiology reports will often describe the overall process as progressive disease while the actual tumor may be stable or shrinking. Investigators are referred to the strict criteria for progressive disease in Section 11 of this protocol to avoid such mis-characterization.

**(7/27/10)** The consequences of bronchial toxicity, e.g., cough, dyspnea, hypoxia, impairment of pulmonary function test parameters, pleural effusion or pleuritic pain (associated with collapse), should all be graded according to the Common Terminology Criteria for Adverse Events (CTCAE), v. 4; MedDRA, v. 12.0.

**6.9.4** Lung Injury

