## 6.10.2 **SPECIAL REPORTING FOR THIS STUDY**

Immediately upon identification of a serious adverse event (SAE) as defined in Section 13.1.1 and provided below), the site will telephone the 24-hour RTOG AE Report Line: [contact]. The site will provide details of the SAE to RTOG Headquarters and will be instructed to fax the completed lung adverse event form (AE), [contact] within 24 hours of discovery of the adverse event. The AE form is available on the RTOG web site, with all of the 0813 forms. The site also will report the adverse event via AdEERS (see Section 6.10).

All reported adverse events will be reviewed by 1 of 3 designated radiation/medical oncologists not associated with this study within 2 business days of receipt of all supporting documentation. The determination of those adverse events as a study DLT will be made by the designated independent reviewer.

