### **Serious Adverse Events That Require Special Reporting (7/27/10)**

- Grade 3-5 Cardiac Disorders
  - Pericardial effusion
  - Pericarditis
  - Restrictive cardiomyopathy
- Grade 4-5 Gastrointestinal Disorders
  - Dysphagia
  - Esophagitis
  - Esophageal fistula
  - Esophageal obstruction
  - Esophageal perforation
  - Esophageal stenosis
  - Esophageal ulcer
  - Esophageal hemorrhage
- Grade 3-5 Nervous System Disorders
  - Brachial plexopathy
  - Recurrent laryngeal nerve palsy
  - Myelitis
- Respiratory, Thoracic, and Mediastinal Disorders, Grade 3-5, except as noted below
  - Atelectasis (grade 4-5 only)
  - Bronchopulmonary hemorrhage
  - Mediastinal hemorrhage
  - Pleural hemorrhage
  - Tracheal hemorrhage
  - Bronchial fistula
  - Pulmonary fistula
  - Bronchopleural fistula
  - Tracheal fistula
  - Hypoxia (provided grade 3 is worse than baseline)
  - Bronchial obstruction
  - Tracheal obstruction

- Pleural effusion
- Pneumonitis
- Pulmonary fibrosis
- Changes in Pulmonary Function Tests per the SBRT Pulmonary Toxicity Scale (see Section 6.9.5). Grade 3-5
  - FEV1 decline
  - Forced Vital Capacity decline
- Any Grade 5 adverse event attributed to treatment

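### The closed DLT list catches great-vessel injury only if it bleeds, presents as another listed event or is fatal, so a non-fatal grade 3-4 aneurysm would be weighted as DLT-free

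*Protocol*

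**What the plan says.** Section 1.3.1 says that the organs "expected to be determinants of dose-limiting toxicity are lung, central airway/bronchi, esophagus, heart, great vessels, spinal cord, and nerves". Section 6.5.2.10 has the aorta or vena cava contoured, and Table 3 has a row for "Great vessels, non-adjacent wall" with aneurysm as the avoidance endpoint. The volume limit in that row (less than 10 cc at 47 Gy) is a planning suggestion. Only the point maximum of 105% of prescription is enforced.

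Section 13.1.1 defines a DLT as a grade 3 or worse event within 1 year of the start of SBRT that "is possibly, probably, or definitely related to treatment, and is related to the following specific symptoms". The list that follows covers cardiac and pericardial, esophageal, nerve and cord, and respiratory and mediastinal terms, and FEV1 and FVC decline. The respiratory and mediastinal group includes four hemorrhages and four fistulas. The list ends with any fatal event attributed to treatment. The special-reporting list in 6.10.2 has the same terms.

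Under 13.4.1 a patient without a DLT contributes with weight u/12, where u is months of follow-up, and a patient with a DLT has weight 1. Related grade 3 or worse events in the first year that are not DLTs are tabulated as a secondary endpoint (13.5.3.1).

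**The concern.** Dose assignment (13.4.2) and the MTD (13.5.1.1) respond only to counted DLTs. The great vessels are an organ that the protocol itself expects to be dose-limiting, yet the injury it plans against, aneurysm, is not among the events that count. A related, non-fatal grade 3-4 aneurysm or other wall injury that does not bleed or present as another listed event fits no term.

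The patient would then supply evidence that the dose is tolerated, with a weight that rises to 1 at 12 months. The error runs in one direction, towards higher doses, in patients whose tumors lie close to the mediastinum. The enforced planning limit does not offset this because it scales with the dose level: 1.05 × 50 = 52.5 Gy at Level 5 and 1.05 × 60 = 63 Gy at Level 9.

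**Working it through.** **Step 1. Organs in 1.3.1 against terms in 13.1.1**

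| Organ in 1.3.1 | Terms in 13.1.1 |
|---|---|
| Lung | pneumonitis, pulmonary fibrosis, FEV1/FVC decline |
| Central airway/bronchi | bronchial and tracheal obstruction, fistulas |
| Esophagus | eight terms, grade 4-5 |
| Heart | pericardial effusion, pericarditis, restrictive cardiomyopathy |
| Spinal cord | myelitis |
| Nerves | brachial plexopathy, recurrent laryngeal nerve palsy |
| Great vessels | no wall-injury term; reached only through hemorrhage, a fistula or other listed presentation, or death |

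**Step 2. The model**

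Inputs from 13.4.1 and Table 13.1: logit p = 3 + α·d, with d = logit(p0) − 3 and prior α ~ Normal(1, 0.3). The likelihood contribution is p for a DLT and 1 − w·p otherwise, with w = u/12. P(DLT) is taken at the posterior mean of α. The next dose is the highest level with P ≤ 0.20, at most one level up, after at least 1 year of cumulative observation at the current level (13.4.2).

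Check against the protocol's own figure: at α = 1, logit p = logit(p0), so Level 5 returns the 0.08 of Table 13.1. There d = ln(0.08/0.92) − 3 = −5.442.

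**Step 3. One event while data are sparse**

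Four patients are at Level 5, each with the same follow-up, and one has the vessel injury. Section 13.4.2 expects the required year of observation to come from no more than four patients with at least 3 months each.

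| Months each | Counted: mean α, P at Level 5, next level | Not counted: mean α, P at Level 5, next level |
|---|---|---|
| 3 | 0.735, 0.269, Level 3 | 1.045, 0.064, Level 6 |
| 6 | 0.785, 0.219, Level 4 | 1.082, 0.053, Level 6 |
| 9 | 0.834, 0.177, Level 5 | 1.114, 0.045, Level 6 |
| 12 | 0.878, 0.145, Level 6 | 1.139, 0.039, Level 6 |

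First row, counted:
- Level 5: 3 + 0.735 × (−5.442) = −1.000, so P = 0.269.
- Level 4: 3 + 0.735 × (−5.944) = −1.369, so P = 0.203, just over the limit.
- Level 3: 3 + 0.735 × (−6.178) = −1.541, so P = 0.176.

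First row, not counted: 3 + 1.045 × (−5.442) = −2.687, so P = 0.064. Only the one-level rule then holds the next patient at Level 6.

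**Step 4. One event with more data**

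- Six fully observed patients at Level 5: P at Level 5 is 0.110 counted and 0.033 not counted (α 0.936 and 1.171). The next level is 6 either way.
- Six fully observed at Level 5 plus four at Level 6 with 3 months each, event at Level 6, one earlier DLT at Level 5: P at Level 6 is 0.212 counted (next Level 5) and 0.122 not counted (next Level 7).
- The same with no earlier DLT: 0.109 and 0.041, next Level 7 either way.
- Trial end, 15 patients at each of Levels 5-9, DLTs 2, 2, 4 or 3, 4, 4 (16 or 15 in total): P at Level 7 is 0.211 or 0.197 (α 0.897 or 0.915). Level 7 is closest to 0.20 either way, so the MTD does not change.

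**The case against.** The strongest reply is that the list is organized by toxicity class and already covers the main severe presentations of vessel injury. Bleeding into the mediastinum is a listed grade 3-5 event, fistulas are listed, and fatal rupture falls under the grade 5 catch-all. What remains is narrow. This stands. A reader might infer that great-vessel toxicity is left out of the DLT definition altogether, and the list does not support that.

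A reader might also infer that 1.3.1 and 13.1.1 contradict each other. They do not. Section 1.3.1 is background on dose-volume limits and does not promise a DLT term for each organ. Section 6.9 says "There is concern about RT effects on organs at risk, most notably central airway, esophagus and heart/pericardium", and the list is plainly selective: DLCO decline, grade 3 esophageal events, grade 3 atelectasis and skin ulceration are also absent. The omission may be a choice. Even so, lung and esophagus keep other terms, and 1.3.1 does not name skin as an expected determinant of DLT.

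Nor would the event go unseen. Grade 4-5 serious events need 24-hour notification whatever their cause. So do related grade 3-5 serious events after 30 days. The safety board meets twice a year and as needed. Section 6.10.2 says "All reported adverse events will be reviewed by 1 of 3 designated radiation/medical oncologists not associated with this study", which could reach an unlisted event. Section 13.1.1 is narrower: "All reported serious adverse events (SAEs) listed above will be reviewed by 1 of 3 designated senior radiation/medical oncologists". It also treats only listed events as DLTs pending that review. Neither section gives the reviewer a qualifying term for aneurysm, so visibility does not put the event into the model.

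Finally, any binary outcome moves a sparse reassessment model, and the largest contrast (Level 3 against Level 6) turns on P = 0.203 at Level 4 against a limit of 0.20. Both points are fair. The examples show what one event can do, not how often it would happen.

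**Conclusion.** The point holds as a narrow gap that is cheap to close. A treatment-related, non-fatal grade 3-4 great-vessel wall injury with no listed presentation would be weighted as DLT-free follow-up. One such event can change the next dose when patients are few and partly observed, or when it follows an earlier DLT. In the other worked cases the next level is the same either way, and the MTD in the trial-end example does not move.

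A reader might go further and infer a materially biased MTD. That needs an event rate, which the protocol does not give. An illustrative simulation (250 runs per case, DLT-td scenario) assumed a constant unlisted vessel risk. At 2%, the mean true total risk at the selected MTD was 0.205 uncounted and 0.195 counted; at 5% it was 0.236 and 0.196. Nothing in the protocol supports either rate, so no average effect is claimed, and it is probably small.

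The sparse-data results assume the model exactly as written in 13.4, with P taken at the posterior mean of α.

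**What to change.** Add to the lists in 13.1.1 and 6.10.2: great-vessel (aorta or vena cava) injury such as aneurysm, grade 3-5, graded by the CTCAE v4 general severity criteria. Naming the grading basis matters because a broad term for vessel-wall injury would otherwise have no defined grade.

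Send any such event already recorded as non-DLT to the existing independent reviewer, and update the model before the next assignment if it is confirmed.

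The cost is one term in two lists, with the same forms and reviewers. The sample size does not change (75/0.80 = 93.75, rounded up to 94). The downside is slightly slower escalation if such events occur.
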